2. *on-treatment period*: from date of first administration of study treatment to 30 days after date of last actual administration of any study treatment (including start and stop date)
3. *post-treatment period*: starting at day 30 + 1 after last administration of study treatment

If a clear assignment to the pre-, on-, or post-treatment period cannot be made, e.g., in case of specific incomplete dates, then the respective data will be assigned to the on-treatment period.

Safety summaries (tables, figures) include only data from the on-treatment period with the exception of baseline data which will also be summarized where appropriate (e.g. change from baseline summaries). In addition, a separate summary for death including on-treatment and post-treatment deaths will be provided. In particular, summary tables for adverse events (AEs) will summarize only on-treatment events, with a start date during the on-treatment period (*treatment-emergent* AEs).

However, all safety data (including those from the post-treatment period) will be listed and those collected during the pre-treatment and post-treatment period will be flagged.

Windows for multiple assessments

In order to summarize ECG data collected over time (including unscheduled visits), the assessments will be time slotted. The following general rule will be applied in creating the assessment windows: If more than 1 assessment is done within the same time window, the assessment performed closest to the target date will be used. If 2 assessments within a time window are equidistant from the target date, then the earlier of the 2 assessments will be used. If multiple assessments occur on the same date then the worst case will be used except for ECGs. Three ECGs are targeted to be measured at the protocol-defined (nominal) time-points. If a subject has more than one measurement at a specific time point, the average of all available measurements associated with the nominal time point will be used for the analysis. Data from all assessments (scheduled and unscheduled), including multiple assessments, will be listed.

Last contact date

The last contact date will be derived for subjects not known to have died at the analysis cut-off [REDACTED] using the last complete date among the following.

Table 2-1 Last contact date data sources

Source data	Conditions
Last known date patient alive collected on the 'Survival information' eCRF	Subject status is reported to be unknown or lost to follow-up

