Date of assessment collected on the 'Survival information' eCRF	Subject status is reported to be alive and missing last known date patient alive
Start/end dates of anti-neoplastic therapies administered after study treatment discontinuation	Non-missing medication or procedure term
Study medication start/end dates from DAR eCRF	Non-missing dose; zero doses are allowed
Date of discontinuation from 'End of Treatment' eCRF and 'End of post-treatment phase' eCRF	None
Start/End dates of AE	Non-missing verbatim AE term
Tumor (RECIST) assessment date	Evaluation is marked as 'done'
Laboratory/PK collection dates	Sample collection marked as 'done'
Vital signs, ECG assessment dates	At least one non-missing parameter value
Performance status dates	Non-missing performance status

The last contact date is defined as the latest complete date from the above list or the cut-off date whichever comes first. The cut-off date will not be used for last contact date, unless the subject was seen or contacted on that date. No date post cut-off date will be used. Completely imputed dates (e.g. the analysis cut-off date programmatically imputed to replace the missing end date of a dose administration record) will not be used to derive the last contact date. Partial date imputation is allowed for event (death)/censoring if coming from 'Survival information' eCRF.

The last contact date will be used for censoring of subjects in the analysis of overall survival.

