PFS is defined as the time from the date of first administration of study treatment to the date of the first documented progression or death due to any cause. PFS will be based on local investigators or BIRC review of tumor assessments and using RECIST 1.1 criteria (see [CSP Appendix 1]). PFS will be censored at the date of the last adequate tumor assessment if no PFS event is observed prior to the analysis cut-off date [REDACTED] or before the start of the new anti-cancer therapy date, whichever is earlier. (See Section 2.7.3 for additional details regarding censoring rules and determination of date of last adequate tumor assessment, see Section 2.5.2.1 regarding exceptions in determining anti-cancer therapy usage). Discontinuation due to disease progression (collected on the ‘End of treatment’ and ‘End of post treatment follow up’ disposition pages without supporting objective evidence satisfying progression criteria per RECIST 1.1 will not be considered disease progression for PFS derivation. Clinical deterioration will not be considered as a qualifying event for progression.

Overall survival

OS is defined as the time from date of first administration of study treatment to date of death due to any cause. All deaths occurring on or before the efficacy cut-off date will be used in the OS analysis. If a subject is not known to have died at the time of the analysis, the OS time will be censored at the date of last contact.

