5.1 Imputation rules

5.1.1 Investigational drug

The following rule should be used for the imputation of the dose end date for a given study treatment component:

Scenario 1: If the dose end date is completely missing and there is no EOT page and no death date, the subject is considered as on-going

The subject should be treated as on-going and the cut-off date should be used as the dose end date. Scenario 1 should not be applicable for the final CSR. All subjects in the current analysis have the EOT page completed before DBL for the final CSR.

Scenario 2: If the dose end date is completely or partially missing and the EOT page is available

- Case 1: The dose end date is completely missing and the EOT completion date is complete, then this latter date should be used
- Case 2: Only year (YYYY) of the dose end date is available and YYYY < the year of EOT date, then use 31DECYYYY

- Case 3: Only year (YYYY) of the dose end date is available and YYYY = the year of EOT date, then use EOT date
- Case 4: Both year (YYYY) and month (MMM) are available for dose end date and YYYY = the year of EOT date and MMM < the month of EOT date, then use last day of the Month (MMM)

All other cases should be considered as a data issue and the statistician should contact the data manager of the study.

After imputation, compare the imputed date with start date of treatment

- If the imputed date is < start date of treatment, then use the treatment start date
- Otherwise, use the imputed date

Subjects with missing start dates are to be considered missing for all study treatment component related calculations and no imputation will be made. If start date is missing then end-date should not be imputed.

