5.1.3 Other imputations

Incomplete date of initial diagnosis of cancer and date of most recent recurrence

Missing day is defaulted to the 15th of the month and missing month and day is defaulted to 01Jan.

If because of this imputation the chronology of the events is altered then the imputation should be made to the minimum value up to where chronology remains unchanged. E.g. if due to imputation the date of most recent recurrence becomes prior to the initial diagnosis date then it should be set to initial diagnosis date.

Incomplete assessment dates for tumor assessment

All investigation dates (e.g. MRI scan, CT scan) must be completed with day, month and year. If one or more assessment dates are incomplete but other investigation dates are available, this/these incomplete date(s) are not considered for calculation of the assessment date and assessment date is calculated as the latest of all investigation dates (e.g. MRI scan, CT scan) if the overall response at that assessment is CR/PR/SD/UNK. Otherwise – if overall response is progression – the assessment date is calculated as the earliest date of all investigation dates at that evaluation number. If all measurement dates have no day recorded, the 1st of the month is used. If the month is not completed, for any of the investigations, the respective assessment will be considered to be at the date which is exactly between the previous and following assessment. If a previous and following assessment is not available, this assessment will not be used for any calculation.

Applying the cut-off to tumor assessment

For tumor related assessments, if an evaluation has some assessments done prior to cut-off date and others after the cut-off date, then the evaluation is considered post-cut-off date and will be excluded from analysis.

Incomplete or missing death date

For cases when either day is missing or both month and day are missing for the date of death, the following imputation rules will be implemented:

- If only day is missing, then impute the 15th day of the month and year of death

- If both day and month are missing, then impute 01Jul of the year of death

Prior antineoplastic therapies date imputation

- Start dates
The same rule which is applied to the imputation of AE/concomitant medication start dates will be used with the following exception:
 - If month and day are missing and the available year = year of study treatment start date, then impute with study treatment start date – 1

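### The rule for partial death dates has no floor, so a death can be dated before the subject was last known alive, or even before first dose.

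*SAP*

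**What the plan says.** SAP Section 5.1.3, under the paragraph on incomplete or missing death dates, gives two rules with no condition attached:

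- For an unknown day: "If only day is missing, then impute the 15th day of the month and year of death".
- When the month is unknown as well, the death is dated to 01 July of the recorded year.

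No redaction is visible in that paragraph.

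Imputed death dates do enter the analysis. Section 2.1.4 says "Partial date imputation is allowed for event (death)/censoring if coming from" the survival information eCRF. The same section restricts the one date that could act as a floor: "The last contact date will be derived for subjects not known to have died at the analysis cut-off".

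Section 2.7.1 shows where the date is used. For overall survival, "OS is defined as the time from date of first administration of study treatment to date of death due to any cause". PFS runs from the same start "to the date of the first documented progression or death due to any cause". DOR also ends at progression or death.

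Some neighbouring rules do carry a guard. For dose end dates, Section 5.1.1 says "If the imputed date is < start date of treatment, then use the treatment start date". In Section 5.1.3, the diagnosis and recurrence dates must keep their order, and prior-therapy end dates are capped at the start of study treatment.

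**The concern.** A mid-period default is a reasonable guess when nothing else is known about the date. For a trial subject a good deal else is known: dosing, scans, laboratory samples, vital signs and survival contacts all show that the subject was alive on a given day. A rule that ignores them can produce sequences that cannot have happened:

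- death before a scan or visit that the subject attended;
- death before the first dose, which starts the OS and PFS clocks;
- with a year-only date, death before the response that starts the DOR clock.

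In the first case the event time is too short. In the second it is negative, and the programmer has to improvise after database lock or the event is lost. Section 1.1.2 plans Phase II groups of about 5, about 30 and at least 40 subjects, so a single misdated early death could be visible in a group's curve.

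**Working it through.** The SAP states no figure on this point, so there is none to reproduce. The check applies the two rules literally.

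**Inputs.** Imputed date = 15th of the recorded month, or 01 July of the recorded year (Section 5.1.3). Study day = event date − start date + 1 on or after start, and event date − start date before start (Section 2.1.4). The calendar dates below are invented for illustration.

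**Largest displacement before a known-alive date**

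- Day missing: last seen alive on the 31st, imputed to the 15th: 31 − 15 = 16 days.
- Day and month missing: last seen alive on 31 December, imputed to 01 July: 30 + 31 + 30 + 31 + 30 + 31 = 183 days.

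**Worked cases**

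| Known fact | Recorded death | Rule date | Result | With a floor |
|---|---|---|---|---|
| Alive 28 Mar 2018 | Mar 2018 | 15 Mar 2018 | 28 − 15 = 13 days before seen alive | 28 Mar 2018 |
| Alive 20 Nov 2018 | 2018 | 01 Jul 2018 | 30 + 31 + 30 + 31 + 20 = 142 days before seen alive | 20 Nov 2018 |
| First dose 20 Mar 2018 | Mar 2018 | 15 Mar 2018 | study day 15 − 20 = −5 | day 1 or later |
| First dose 01 Sep 2018 | 2018 | 01 Jul 2018 | study day −(31 + 31) = −62 | day 1 or later |

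**How often, given a partial date.** The SAP gives no data for this, so the following is an assumption. Death is uniform over a 365-day year, and the gap from last known-alive date to death is uniform on 0 to G days. G = 91 is about the three-month survival follow-up interval, and G = 105 is that interval plus two weeks (Section 2.7.3: 3 × 30.4375 + 14 = 105.3125 days). The share of partial dates imputed before the last known-alive date is:

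| G (days) | Day missing | Day and month missing |
|---|---|---|
| 14 | 27.7% | 48.2% |
| 30 | 13.5% | 46.0% |
| 91 | 4.5% | 37.7% |
| 105 | 3.9% | 35.8% |

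These shares apply only to deaths with a partial date, not to all deaths.

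**Does another passage repair the rule?**

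- The sentence on preserving chronology in Section 5.1.3 stands under the diagnosis and recurrence heading, and its example concerns only those dates.
- The closing catch-all of Section 5.1.3 is for scenarios that no rule covers. A partial death date is covered.
- Last contact date is not derived for decedents.

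No visible passage supplies the floor.

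**The case against.** The strongest reply is that little rests on this. The primary endpoints are DLTs, ORR, and safety and tolerability in Group 4 (Table 1-1), and ORR does not use death dates. OS, PFS and DOR are secondary and summarized by Kaplan-Meier without a comparison. Survival follow-up about every three months makes a year-only death date less likely, and a missing day costs at most 16 days. A negative time also needs a death in the same month or year as first dose. There may be no partial death dates at all. All of this stands, and it limits the severity.

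The death rule is also not the only unguarded one. In Section 5.1.3, tumor assessment dates with no day go to the first of the month without comparison with any other date. That stands too, so the case rests on what the death rule produces, not on its being a lone exception.

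Some stronger readings are tempting, but the SAP does not support them:

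- *The cut-off is ignored.* Section 2.7.1 says "All deaths occurring on or before the efficacy cut-off date will be used in the OS analysis". How a partial date is compared with the cut-off is not visible, but Section 2.1.1, which the amendment log says was updated for the efficacy cut-off, is redacted.
- *Deaths are misclassified as on- or post-treatment.* Section 2.1.4 assigns data with unclear incomplete dates to the on-treatment period.
- *Survival is biased in a known direction.* Dates that are too early shorten survival, while unusable early deaths would lengthen it. No net direction can be shown.

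**Conclusion.** The point holds for the missing floor. As written, the rule can date a death up to 16 days (day missing) or up to 183 days (day and month missing) before the subject was known to be alive. It can also date a death before first dose when both fall in the same month or year. These limits follow from the calendar and need no assumption beyond a literal reading of Section 5.1.3. How often this happens cannot be established: the percentages above rest on assumed uniform distributions, and the number of partial death dates is not given.

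The effect is confined to the descriptive OS, PFS and DOR estimates and is probably small. Severity is minor to moderate. A reader might infer that the plan cannot proceed without the change, but no primary endpoint and no decision rule depends on it.

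**What to change.** In Section 5.1.3, add for decedents a last known-alive date: the latest complete date on which the subject was verifiably alive. Suitable sources are dates of non-zero doses, visits, scans, laboratory samples, vital signs or ECG, and survival contact.

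Table 2-1 should not be taken over whole. Administrative discontinuation dates, zero-dose records and AE end dates can fall on or after death and would push the death too late.

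Then set:

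death date = max(date from the current rule, last known-alive date), kept within the recorded month or year.

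Because the date of first dose is itself a known-alive date, the result is never before first dose. No extra day should be added, since a subject can be seen and die on the same day. If the last known-alive date lies after the recorded month or year, the records conflict and should be queried rather than imputed. Use the same death date for OS, PFS and DOR.

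The cost is about two sentences in Section 5.1.3 and a small derivation in the dataset program. No new data are needed.

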- End dates
 - If day is missing, imputed date = min(reference end date, last day of the month)
 - If month and day are missing, imputed date = min(reference end date, 31Dec)

Reference end date will be the start date of study treatment.

If the end date is not missing and the imputed start date is after the end date, use the end date as the imputed start date. If both the start date and the end date are imputed and if the imputed start date is after the imputed end date, use the imputed end date as the imputation for the start date.

Post-treatment antineoplastic therapies date imputation

For new antineoplastic (ANP) therapies starting after study treatment was discontinued or starting while study treatment was still ongoing (protocol deviation), a missing or partial start date of this new therapy will be imputed as specified in [Table 5-3](#).

The complete (imputed) dates are required for censoring of efficacy endpoints. Therefore, partial or missing start dates will only be imputed for the first such therapy. Partial or missing end dates of the first new therapy and any partial or missing dates of second or later new antineoplastic therapies will not be imputed.

Table 5-3 Imputation of start dates for post-treatment antineoplastic medications

Missing element	Rule
Day	
 • If available year \geq year of study treatment end date then ANP start date = max(study treatment end date + 1, 01MonYYYY) • If available year < year of study treatment end date then ANP start date = max(study treatment start date + 1, 01MonYYYY)
Day, month	
 • If available year = year of study treatment end date then ANP start date = min(study treatment end date + 1, 31DecYYYY) • If available year > year of study treatment end date then ANP start date = 01JanYYYY • If available year < year of study treatment end date, 
 • If available year < year of study treatment start date, do not impute • If available year > year of study treatment start date, then ANP start date = 01JulYYYY • If available year = year of study treatment start date and day/month of study treatment start date < 01JulYYYY, then ANP start date = 01JulYYYY

Missing element	Rule
	
 If available year = year of study treatment end date and day/month of study treatment start date \geq 01JulYYYY, then ANP start date = min(middle between the treatment start and end date, 31DecYYYY)

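### SAP Table 5-3 can date a new anti-cancer therapy outside its own recorded month, and one of its branches can never apply

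*SAP*

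**What the plan says.** The subsection of SAP Section 5.1.3 on post-treatment antineoplastic therapies covers therapies begun after study treatment was discontinued and also those "starting while study treatment was still ongoing (protocol deviation"). It gives the purpose: "The complete (imputed) dates are required for censoring of efficacy endpoints". Only the first new therapy has its start date imputed.

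With only the day missing, Table 5-3 has two rules:
- Therapy year equal to or later than the treatment-end year: "ANP start date = max(study treatment end date + 1, 01MonYYYY").
- Therapy year earlier than the treatment-end year: "ANP start date = max(study treatment start date + 1, 01MonYYYY").

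With day and month missing, a therapy year equal to the treatment-end year gives "ANP start date = min(study treatment end date + 1, 31DecYYYY"), and a later year gives 1 January. The remaining branches are nested under "If available year < year of study treatment end date". The last of these begins "If available year = year of study treatment end date and day/month of study treatment start date", followed by the condition that treatment started on or after 1 July. It returns the midpoint of treatment, capped at 31 December. The branch just before it, for treatment starts before 1 July, tests the year of treatment start.

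After the table, the SAP adds that an imputed start later than a recorded therapy end date is replaced by that end date. Scenarios the rules do not cover go to the dataset program and are documented in the PDS.

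**The concern.** The table's stated scope includes therapies begun during treatment, but its day-missing rule for the treatment-end year cannot return a date on or before treatment end. When the recorded month is earlier than the month of treatment end, the imputed date contradicts the part of the date that is known. The second problem is a branch whose condition excludes its parent's, which leaves a gap where a rule was evidently intended.

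Under Section 2.5.2.3, BOR, and hence ORR, uses only assessments made before the new therapy. Under Section 2.7.3, a PFS event after new therapy is censored at the last adequate assessment, and DOR follows the PFS rule (Section 2.7.1). A start date placed too late can admit scans taken under another therapy. The groups are small: one changed response moves ORR by 1/5 = 20 percentage points in Group 2 (about 5 subjects) and by at most 1/40 = 2.5 points in Group 1 or Group 3 (at least 40 each, Section 1.1.2).

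**Working it through.** The plan gives no figure to reproduce. The check applies Table 5-3 literally to worked dates, which are illustrations and not trial data.

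**Day missing, therapy recorded as March 2018, treatment started 15 February 2018**

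| Treatment end | Year comparison | Rule | Imputed start |
|---|---|---|---|
| 20 Nov 2018 | 2018 = 2018 | max(21 Nov 2018, 1 Mar 2018) | 21 Nov 2018 |
| 10 Jan 2019 | 2018 < 2019 | max(16 Feb 2018, 1 Mar 2018) | 1 Mar 2018 |

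In the first row the true start lies between 1 and 31 March. 21 November minus 1 March is 265 days, and 21 November minus 31 March is 235 days. The recorded therapy month is the same in both rows; only the calendar year of treatment end changes the answer. In a non-leap year the largest shift is 365 days (therapy on 1 January, treatment end on 31 December, imputed 1 January of the next year).

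Consequences in the first row:
- A scan between the true start and 20 November counts for BOR when it should not.
- A progression in August counts as an event. With a March start it would be censored at the last adequate scan before the therapy.
- A progression in December is censored either way, but at the last adequate scan up to 21 November instead of the last one before the March start. Progression-free follow-up is lengthened.

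**Day and month missing, therapy recorded as 2017, treatment 15 September 2017 to 20 November 2018**

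1. Year equal to end year? 2017 = 2018: no.
2. Year later than end year? No.
3. Year earlier than end year? Yes, so go to the nested branches.
4. Year before start year (2017 < 2017)? No. Year after start year? No. Year equal to start year with start before 1 July? No, because the start is 15 September.
5. Last branch: year equal to end year? No. No branch applies and no date results.

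With the start year tested in step 5, the result is min(midpoint of treatment, 31 Dec 2017). Treatment spans 431 days, so the midpoint is about day 215, or 18 April 2018, and the imputed start is 31 December 2017.

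The nesting runs across a page break, so the last branch might be read as top level. It then competes with the first bullet. For a therapy recorded as 2018 with the same treatment dates, the first bullet gives 21 November 2018 and the last branch gives 18 April 2018, 217 days apart. The 2017 record still has no rule.

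**Behaviour over many records.** The table was run on 200,000 simulated therapies started during treatment. The inputs are assumptions, not from the documents: treatment start uniform over 3 years, duration uniform over 60 to 999 days, therapy start uniform within treatment. Among day-missing starts in a month before the month of treatment end, about 40% were dated after treatment end (mean shift about 111 days, maximum 363). With a month-and-year comparison this fell to 0%. With only the year recorded, about 11% had no applicable rule. These shares describe the rule once a partial date on an on-treatment therapy exists. They do not estimate how often that happens in this trial.

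**The case against.** The strongest reply is that exposure is narrow. The three main source forms in Section 2.5.2.3 record therapy given since discontinuation of study treatment, and for those treatment end + 1 is a sensible floor. The first error needs a first new therapy, begun during treatment (which the SAP itself calls a protocol deviation), in an earlier month of the treatment-end year, with the day missing. The analysis is descriptive, and the primary objective has already been reported in the primary CSR. All of this stands and keeps the severity low. It does not make the rule right: Section 5.1.3 puts on-treatment starts in scope, and Section 2.5.2.3 also counts certain therapies from the concomitant medication form if begun after the start of study treatment.

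The two safeguards help only in part. The end-date rule needs a recorded therapy end date and then substitutes it. If the March therapy ended on 30 April 2018, the imputed start would be 30 April, still 30 to 60 days late. The PDS clause covers only cases without a rule. It catches the second error without pre-specifying a date, and it does not reach the first, which has a rule.

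Stronger readings that a reader might infer are not supported:
- The unreachable branch does not date therapies after treatment end; it yields no date.
- Subjects who started treatment on or after 1 July are not generally without a rule. The gap also needs only the year recorded, a therapy year equal to the treatment-start year, and treatment ending in a later year.
- The table does not use years alone throughout, since two sub-branches use the day and month of treatment start. What is missing is a month comparison with treatment end.
- The 265 days is the largest shift in the imputed start in the example, not in the censoring date, which is the last adequate scan.
- The effect is not one-sided in favour of the combination. A censored subject can become an event, which can lower the PFS estimate.

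**Conclusion.** Wrong as written, low severity. In the day-missing row, the imputed date is provably outside the recorded month whenever the therapy began during treatment in an earlier month of the treatment-end year. The shift was 235 to 265 days in the example. In the row with day and month missing, one branch is unreachable, or conflicts with the first bullet if read as top level, and one narrow class of dates has no pre-specified value.

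BOR, PFS or DOR changes only if a scan, progression or death falls between the true and imputed starts. The documents give no count of partial dates or of on-treatment therapies. That few subjects are affected is a judgement based on how many conditions must coincide.

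Treatment end + 1 for completely missing dates, and for dates with only the treatment-end year recorded, is not part of this finding. There it is an assumption that no recorded date part contradicts.

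**What to change.** Two changes to Table 5-3:

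1. Day missing: compare month and year, not year alone, with treatment end. If the recorded month and year are the same as or later than those of treatment end, use max(treatment end + 1, first of the recorded month). Otherwise use max(treatment start + 1, first of the recorded month). Table 5-1 in Section 5.1.2 already compares month and year when the day is missing, so this matches the SAP's own practice.
2. Day and month missing, last sub-branch: change end to start in the year condition, so that it pairs with the branch above it.

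A therapy begun in the month of treatment end would still be dated treatment end + 1, at most 31 days late, which is an acceptable convention.

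The cost is two table cells and the matching dataset code. Listing first new therapies with partial start dates, under the old and the new rule, would show at once whether any BOR, PFS or DOR result changes.
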